### 3.2 Rationale

It is expected that the detailed evaluation of peripheral nerve disorders, infections, neutropenia, infusion reactions, and pulmonary disorders will help better understand the safety profile of Adcetris in the routine clinical setting, which will lead to the assessment of the risk-benefit balance of the drug.

The frequencies of peripheral nerve disorders, infections, neutropenia ( $\geq$ Grade 3), infusion reaction, and pulmonary disorder in non-Japanese phase 2 studies (pooled study data from a study in patients with Hodgkin's lymphoma [SG035-0003, 102 patients] and a study in patients with systemic anaplastic large cell lymphoma [SG035-0004, 58 patients]) were 56%, 61%, 20%, 11%, and 6%, respectively.

Observation of infusion reactions with the lowest frequency of  $\geq 10$  patients, aside from pulmonary disorders, with a probability of 95% would require 140 patients, which was therefore determined to be the estimated enrollment. It is estimated that when the number of patients enrolled reaches 140 patients,  $\geq 4$  patients have adverse events of pulmonary disorder with a probability of 95%.

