1.5 Handling of missing data

- As a general rule, missing data will not be imputed.
- In the analysis of the frequency qualitative variables, missing data will be handles as “unknown.” In the analysis of summary statistics of quantitative variables, missing data will be excluded.

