Grade of renal disorder (Grade based on serum creatinine)	None, Grade 1, Grade 2, \geq Grade 3, or unknown
Concurrent peripheral neuropathy	None, Grade 1, Grade 2, Grade 3, Grade 4, or unknown
Weight	<40 kg, <40 to 50 kg, <50 to 60 kg, <60 to 70 kg, or \geq 70 kg
BMI	<18.5 kg/m ² , <18.5 to 25 kg/m ² , <25 to 30 kg/m ² , or \geq 30 kg/m ²
Smoking history	Never, current, past, or unknown

Data item	Category
Prior drug therapy	Absent or present
Prior drug therapy regimen(s)	ABVD, CHOP, and/or other (If more than one drug therapies in the same regimen is used in the same patient, it will be counted as one patient.)
Number of prior drug therapy regimens	-
Days from the month of the completion of the final regimen of prior drug therapy to the date of 1 cycle of treatment with Adcetris (Prior drug therapy: Yes)	-
Prior radiotherapy	Absent or present
Days from the month of the completion of the most recent prior radiotherapy to the date of 1 cycle of treatment with Adcetris (Prior radiotherapy: yes)	-
Prior hematopoietic stem cell transplantation	Absent, present (autologous), present (homologous), present (autologous and homologous), or unknown
Other prior therapies	Absent, present, or unknown
Pregnancy during the observation period (for females only)	Absent or present

(3) Figure/table number
Tables 3-1 to 3.1-3

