5.9.13 Occurrence of adverse drug reactions of pulmonary disorder and infections

(1) Analysis sets to be used

Safety analysis set, safety analysis set (Hodgkin’s lymphoma), and safety analysis set (anaplastic large-cell lymphoma)

(2) Data to be analyzed

The incidence of pulmonary disorders considered related to Adcetris for each CTCAE grade (the worst one) will be calculated by pulmonary disorder and PT. PTs and PT Codes will be presented in ascending order.

In addition, the incidence of pulmonary disorders considered related to Adcetris for each CTCAE grade (the worst one) will be calculated by patient demographics and baseline characteristics.

The CTCAE grade (the worst one) is higher in the order of Grades 5, 4, 3, 2, 1, and unknown. If the same patient has multiple occurrences of pulmonary disorders or there are multiple occurrences of the same PT, the highest CTCAE grade (the worst one) for the patient or PT will be counted once for the category:

Data item	Category
CTCAE Grade (the worst one) for pulmonary disorders	Grade 1, Grade 2, Grade 3, Grade 4, Grade 5, or unknown

Items and categories of patient demographics and baseline characteristics

Data item	Category
History of or concurrent pulmonary disorder	Absent or present
Smoking history	Non-smoker or smoker * Patients other than those who have never smoked will be classified into “smoker.”
Prior radiotherapy	Absent or present

(3) Figure/table number

Tables 5.9.13-1 to 5.9.13-4

5.10 analysis setanalysis setanalysis setList of actions taken with Adcetris in patients experiencing peripheral nerve disorders considered related to Adcetris

(1) Analysis sets to be used

Patients included in the safety analysis set analysis setanalysis setwho experience peripheral nerve disorders considered related to Adcetris

(2) Data to be analyzed

(3) For each patient, a list of the following data items: patient number, diagnosis, action taken or not taken with Adcetris, reason for action taken, date of dosing and dose for each cycle, date of onset of peripheral nerve disorder, CTCAE grade (the worst one), outcome, and the date of outcome. If the

same patient has multiple occurrences of peripheral nerve disorder, all these occurrences will be counted. Figure/table number

Table 5.10

5.11 List of actions taken with Adcetris in patients experiencing neutropenia considered related to Adcetris

(1) Analysis sets to be used

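### The smoking split for pulmonary disorders (SAP 5.9.13) counts patients with unknown smoking history as smokers, contrary to the SAP's own missing-data rule

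*SAP*

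**What the plan says.** SAP 5.9.13 tabulates the incidence of pulmonary disorders considered related to Adcetris, by worst CTCAE grade, against three background factors: history of or concurrent pulmonary disorder, smoking history, and prior radiotherapy. The smoking levels are "Non-smoker or smoker". The footnote to that row says "Patients other than those who have never smoked will be classified into" the smoker category. It has no third level and states no exclusion.

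In SAP 3.1 (baseline table) the levels are "Never, current, past, or unknown", and SAP 5.3 (adverse drug reactions by background factor) uses the same four.

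SAP 1.5 sets the general rule: "As a general rule, missing data will not be imputed". It continues: "In the analysis of the frequency qualitative variables, missing data will be handles as" unknown.

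The other two SAP versions in the file handle pulmonary disorders in 5.9.9, without any split by smoking. Neither supplemental SAP touches the rule.

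**The concern.** A patient whose smoking history is unknown is not recorded as a never-smoker, so the footnote sends that patient to the smoker row. In effect this is a single-value imputation, always in the same direction, in a plan that says it does not impute. SAP 5.9.13 does not present it as an exception or give a reason for it.

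The treatment also differs from comparable tables. Prior transplantation keeps an unknown level in SAP 5.9.2, 5.9.6 and 5.9.7, and premedication keeps one in 5.9.12.

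What is at stake is the meaning of one row. Pulmonary disorder is one of the five events for which the protocol (section 1.0) says additional surveillance was required, and it has the lowest reference rate of the five. Smoking is one of only three factors tabulated for it. With so few cases expected, one or two cases with unknown history would visibly change the incidence shown for smokers.

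**Working it through.** **Inputs from the documents.** Protocol 3.2 gives the planned size (140 patients) and the reference rates, which "were 56%, 61%, 20%, 11%, and 6%, respectively" for peripheral nerve disorders, infections, neutropenia of Grade 3 or higher, infusion reaction and pulmonary disorder. The smoking categories and the missing-data rule are those set out above.

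**Inputs not in the documents (assumptions).** The share with unknown history, u, is taken as 5%, 15% and 30%. Ever-smokers are 45% of patients with known history. Patients with unknown history have the same smoking mix and risks as the rest. The true ever-to-never risk ratio is 3.0.

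**Step 1: the plan's own figures.** With exact binomial tails, P(X ≥ 10 | n = 140, p = 0.11) = 0.952, and 140 is the smallest n that reaches 0.95. This reproduces the stated enrollment. For pulmonary disorder, P(X ≥ 4 | n = 140, p = 0.06) = 0.971, which agrees with the protocol's statement of at least 4 cases. The expected number is 0.06 × 140 = 8.4 cases over both smoking rows. The 6% is a pooled phase 2 frequency, whereas 5.9.13 counts only related events, so the table may hold fewer.

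**Step 2: where each patient goes.**

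| Recorded history | SAP 3.1 and 5.3 | SAP 5.9.13 |
|---|---|---|
| Never | Never | Non-smoker |
| Current | Current | Smoker |
| Past | Past | Smoker |
| Unknown | Unknown | Smoker |

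Only the last line conflicts with SAP 1.5. If any patient is unknown, current plus past in Table 3.1 will not add up to the smoker denominator in 5.9.13.

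**Step 3: illustrative size.** An overall risk of 6% requires a never-smoker risk of p0 = 0.06 / (0.55 + 0.45 × 3) = 0.0316. The ever-smoker risk is then 3 × 0.0316 = 0.0947. Unknowns have the mixed risk, 0.06.

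- Smoker row as a share of all patients: 0.45(1 − u) + u.
- Share of that row with no smoking information: u / [0.45(1 − u) + u].
- Risk shown for smokers: [0.45(1 − u) × 0.0947 + u × 0.06] / [0.45(1 − u) + u].
- Ratio implied by the table: that risk divided by 0.0316.

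| u | Unknown patients of 140 | Smoker row, share of all | Unknowns within the row | Risk shown | Implied ratio |
|---|---|---|---|---|---|
| 5% | 7 | 0.4775 | 10% | 0.0911 | 2.88 |
| 15% | 21 | 0.5325 | 28% | 0.0850 | 2.69 |
| 30% | 42 | 0.6150 | 49% | 0.0778 | 2.46 |

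With unknowns shown separately, the ratio stays at 3.0.

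**Step 4: direction.** The risk shown for smokers is a weighted average of the ever-smoker risk and the risk among unknowns. It is diluted when unknowns have a lower risk than ever-smokers (below 9.5% in this example) and inflated when theirs is higher. The documents do not settle which applies.

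**The case against.** The strongest reply is that very little depends on this row. SAP 5.9.13 names no test, ratio or confidence interval, while the SAP names tests elsewhere when it wants them (5.3, 5.9.5, 5.9.6). The risk ratio used above is therefore a yardstick, not a planned output. Sampling error is also much larger than the shift. Under the same assumptions with no unknowns, 63 ever-smokers and 77 never-smokers would give about 6.0 and 2.4 cases. The standard error of the log ratio is √(1/5.97 − 1/63 + 1/2.43 − 1/77) = 0.74, so the 95% interval for a ratio of 3.0 is about 0.7 to 12.8. The table could neither establish nor exclude a smoking effect under either coding. All of this stands, and it limits the severity.

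A second reply is that the footnote may only have been meant to join past smokers to current ones, with SAP 1.5 still governing truly missing entries. That may be the intention. The wording does not say so, however, and two levels without an exclusion leave unknowns nowhere else to go.

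A third reply is that Table 3.1 shows how many patients have unknown history, so a reader can see how many of them sit in the smoker denominator. That is true, but it does not show how many pulmonary cases they contribute.

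A reader might also infer that 5.3 and 5.9.13 would disagree on who smoked. The documents do not support that reading: 5.3 never defines a smoker group and covers all adverse drug reactions. The inconsistency is in how unknown history is handled.

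**Conclusion.** The point holds as a minor inconsistency. The stated rule in SAP 5.9.13 classes patients with unknown smoking history as smokers, against SAP 1.5 and the four-level coding in 3.1 and 5.3. It contaminates the smoker row of a descriptive table in which about 8 cases are expected, or fewer if only related events are counted.

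The actual size cannot be computed. It depends on the number of unknowns, which the documents do not give, and it is nil if there are none. If unknowns resemble known patients, the dilution is modest: 3.0 reads 2.9, 2.7 or 2.5 under the assumptions above. If cases cluster among unknowns, the contrast could be exaggerated.

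A reader might infer that the rule would hide a real association between smoking and pulmonary disorders. The documents do not support that. The direction of the bias is not fixed, the illustrative ratio stays well above 1 even at 30% unknown, and no inference is planned on this split.

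**What to change.** In SAP 5.9.13, define smoker as current or past and non-smoker as never. Show unknown as a third row outside the comparison, as 1.5, 3.1 and 5.3 already provide for.

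The cost is one footnote and one table row, using data already collected. The small downside is that cases in patients with unknown history leave an already sparse two-group comparison. At 15% unknown and equal risk that is about 0.15 × 8.4 = 1.3 cases. They remain visible in their own row.

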6.0 Efficacy Analysis

6.1 Best response

(1) Analysis set to be used

Patients included in efficacy evaluation who complete best response assessment analysis set

(2) Data to be analyzed

The frequency of the best response after 16 cycles of treatment with Adcetris (or upon discontinuation of treatment with Adcetris) will be analyzed in patients with Hodgkin's lymphoma and patients with anaplastic large-cell lymphoma. In addition, the point estimate of the response rate (CR + CRu + PR) with two-sided 95% confidence interval will be calculated, and a bar chart of the percentage of each category will be generated. Similar analyses will be performed by presence or absence of PET assessment, and a bar chart will be generated. For the handling of best response assessment data, see Section 1.7.

(3) Figure/table number

Table 6.1 and Figure 6.1

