### 10.5 Efficacy

The measures specified below will be analyzed using the efficacy analysis set.

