1.1.2 Efficacy analysis set

In this survey, the efficacy analysis set is defined as patients treated with Adcetris IV Infusion with no major protocol violation and evaluable for efficacy.

Definition

Term	Definition
This/the product	Refers to Adcetris for intravenous drip infusion in this Statistical Analysis Plan.
SOC	MedDRA/J System Organ Class
HLGT	MedDRA/J High Level Group Term
PT	MedDRA/J Preferred Term
LLT	MedDRA/J Lowest Level Term
Patients registered	Patients whose registration has been approved
Patients whose case report forms are available	Patients whose case report forms have been collected
Patients whose case report forms are not available	Patients registered but whose case report form have not been collected
Fixed patients	Patients whose case report forms are available, with the date of case report form completion entered in the PMS system
Non-fixed patients	Patients whose case report forms are available, with the date of case report form completion not entered in the PMS system
Safety analysis set	Fixed patients included in the safety analysis set
Safety analysis set (Hodgkin's lymphoma)	Patients included in the safety analysis set whose diagnosis is Hodgkin's lymphoma
Safety analysis set (anaplastic large-cell lymphoma)	Patients included in the safety analysis set whose diagnosis is anaplastic large-cell lymphoma
Patients excluded from the safety analysis set	Fixed patients excluded from the safety analysis set
Efficacy analysis set	Patients included in the safety analysis set who are also included in the efficacy analysis set
Patients excluded from the efficacy analysis set	Patients included in the safety analysis set who are excluded from the efficacy analysis set
Patients completing treatment	Patients completing 16 cycles of treatment with Adcetris
Patients discontinuing treatment	Patients not completing 16 cycles of treatment with Adcetris

Term	Definition
Adverse drug reactions, etc.	
Refers to “adverse drug reactions and infections.”
 
Adverse events not considered “not related” to Adcetris by the investigator.
 
In this Statistical Analysis Plan, the term “adverse drug reactions and infections” is used in titles and the term “adverse drug reactions, etc.” is used in text and tables.

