2.0 Patient Disposition (Patient Disposition Diagram)

(1) Analysis set to be used

Patients registered

(2) Data to be analyzed

Data to be analyzed includes the numbers of patients registered, institutions with patients registered, patients whose case report forms are available/not available, fixed/non-fixed patients, patients included in/excluded from the safety analysis set, and patients included in/excluded from the efficacy analysis set.

For the number of institutions with patients registered, the same institutions with different departments should not be counted more than once.

For patients whose case report forms are not available, the number of patients by reason for unavailability will be calculated. The reason for unavailability should be transfer or health problems of the investigator or other.

For patients included in safety evaluation, the number of patients by primary disease (Hodgkin's or anaplastic large-cell lymphoma or other) and the overall number of patients will be calculated. For patients included in efficacy evaluation, the number of patients by primary disease (Hodgkin's or anaplastic large-cell lymphoma) and the overall number of patients will be calculated.

For patients excluded from the safety/efficacy analysis set, the number of patients by reason for exclusion will be calculated, and a patient list will be generated.

The selection of patients to be included in safety evaluation and those who are to be included in efficacy evaluation will be made as shown below:

Criterion	Safety evaluation	Efficacy evaluation
Adcetris has never been administered [found afterwards]	×	×
No data for safety evaluation (data to determine the presence or absence of adverse events) are available	×	×
Non-primary disease	○	×

○: Included, ×: Excluded

(3) Figure/table number

Figure 2.0 and Table2.0

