2.0 Patient Disposition (Patient Disposition Diagram)

(1) Analysis set to be used

Patients registered to this specified drug-use survey

(2) Data to be analyzed

Data to be analyzed includes the numbers of patients registered, institutions with patients registered, patients whose case report forms are available/not available, fixed/non-fixed patients, patients included in/excluded from the safety analysis set, and patients included in/excluded from the efficacy analysis set.

For the number of institutions with patients registered, the same institutions with different departments should not be counted more than once.

For patients whose case report forms are not available, the number of patients by reason for unavailability and the total number of patients will be calculated.

For patients excluded from the safety/efficacy analysis set, the number of patients by reason for exclusion and the total number of patients will be calculated.

It will be determined as follows whether patients meeting the following criteria should be included or excluded:

Criterion	Registration	Safety evaluation	Efficacy evaluation
Duplicate registration (of the same patient) [found afterwards]	×	×	×
Non-primary disease	○	○	×
Adcetris has never been administered [found afterwards]	×	×	×
No definite safety evaluation results are available	○	×	×
No definite efficacy evaluation results are available	○	○	×
No case report form is available	○	×	×

○: Included, ×: Excluded

(3) Figure/table number

Figure 2.0 and Table2.0

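### SAP 6.1 computes the response rate only in patients with a completed response assessment and plans no count of the rest, so the rate is too high if unassessed patients respond less often

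*SAP*

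**What the plan says.** - **Protocol 10.5 (Efficacy)**, which covers best response and overall survival: "The measures specified below will be analyzed using the efficacy analysis set". It does not restrict the set to assessed patients.
- **SAP 6.1 (Best response)** names a narrower set: "Patients included in efficacy evaluation who complete best response assessment analysis set". On that set, by disease, the response categories are tabulated and "the point estimate of the response rate (CR + CRu + PR) with two-sided 95% confidence interval will be calculated". No other response rate is planned.
- **SAP 6.3 (Overall survival)** uses all patients in efficacy evaluation, without the extra condition.
- **SAP 1.1.2**: "the efficacy analysis set is defined as patients treated with Adcetris IV Infusion with no major protocol violation and evaluable for efficacy". Evaluable is not defined further.
- **SAP 2.0 (Patient Disposition)** lists three grounds for leaving the efficacy evaluation: never treated, no safety data, and a disease other than the target ones. A missing response assessment is not among them. The section also asks for counts by disease: "For patients included in efficacy evaluation, the number of patients by primary disease" and the overall number.
- **SAP 1.5 (Handling of missing data)**: "As a general rule, missing data will not be imputed". For categorical tables, "In the analysis of the frequency qualitative variables, missing data will be handles as" unknown.
- **The two other SAP versions in the file**, apparently earlier, list "No definite efficacy evaluation results are available" as a ground for exclusion from efficacy. The difference is not itself an error. It only means that the current table no longer settles the matter.

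**The concern.** The denominator depends on whether a scan-based assessment was recorded, and that may be related to outcome. Response is recorded after 16 cycles or at discontinuation, in routine practice at about 100 institutions. Patients who are lost to follow-up, move to another hospital or die early may have no assessment. If such patients respond less often, an assessed-only rate overstates response in the treated population.

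The second problem is visibility. The rule in SAP 1.5 would put missing assessments on their own row, but 6.1 removes these patients before the table is built. A reader could recover their number only by subtracting the 6.1 denominators from the counts in SAP 2.0, and would not learn who they are. It is also unclear whether they belong to the efficacy set at all.

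**Working it through.** **The plan's own figures.** The documents state no expected response rate and no expected share of unassessed patients. The only derived figure is the enrolment of 140 in Protocol 3.2, which rests on infusion reactions at 11%. It reproduces: the smallest n with P(X ≥ 10) ≥ 0.95 is 140 (P = 0.952). It has no bearing on the response rate.

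**Are unassessed patients in the efficacy set?** There are two readings.
1. The evaluable condition in SAP 1.1.2 already removes them. The extra condition in 6.1 would then be redundant, and the table in 2.0 would lack the matching criterion.
2. They stay in the set, count in 6.3, and drop out only in 6.1 and 6.2. This fits the table in 2.0 and the wording of 6.1 better.

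On either reading they are outside the response-rate denominator.

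**Does another section report them?** SAP 6.1 and 6.2 refer to a Section 1.7 for handling best response data. No section is printed under that number. The likely target is 1.6 (Others), whose only rule on best response concerns a missing imaging date, not a missing assessment.

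**Size.** Let p be the response rate in assessed patients, q the rate in unassessed patients and m the unassessed share. The rate over everyone is (1 − m)p + mq, so

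assessed-only rate − rate over everyone = m(p − q).

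The assumptions, which are not in the documents, are p = 50–80% and m = 5–20%.

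- q = 0 (none responded): the gap is mp, from 0.05 × 0.50 = 2.5 points to 0.20 × 0.80 = 16 points too high.
- q = p/2: half of that, 1.25 to 8 points too high.
- q = p: no gap.
- q = 1 (all responded): the gap is m(1 − p), from 0.05 × 0.20 = 1 point to 0.20 × 0.50 = 10 points too low.
- m = 0: no gap.

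**Illustration by disease.** This assumes 140 patients split like the two phase 2 studies in Protocol 3.2 (140 × 102/160 = 89.25 and 140 × 58/160 = 50.75, so 89 and 51), about 10% unassessed and about 70% response. Intervals are exact (Clopper-Pearson) 95%.

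| | Assessed only | All, unassessed as non-response | All, every unassessed patient responded |
|---|---|---|---|
| Hodgkin's (9 unassessed) | 56/80 = 70.0% (58.7–79.7) | 56/89 = 62.9% (52.0–72.9) | 65/89 = 73.0% (62.6–81.9) |
| Anaplastic large cell (5 unassessed) | 32/46 = 69.6% (54.2–82.3) | 32/51 = 62.7% (48.1–75.9) | 37/51 = 72.5% (58.3–84.1) |

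The planned rate is 7.1 and 6.8 points above the conservative one, and 3.0 points below the optimistic one in both diseases. At 70% response, each unassessed patient counted as a non-responder moves the rate by 0.70/89 = 0.79 points or 0.70/51 = 1.37 points.

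**The case against.** The strongest case is that this is a minor reporting matter. Efficacy is collected for reference in a single-arm survey, 6.1 plans no test, and no decision or sample size rests on this rate. Every patient has a planned collection point, because Appendix 1 of the protocol marks best response both after 16 cycles and at discontinuation. Nothing in the documents shows that many assessments will be missing, and the percentages above are assumptions. The 89/51 split comes from non-Japanese studies and says nothing about the case mix here. All of this stands. It limits the weight of the point but does not answer it.

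Some details also stand:
- Table shells are not in the file, so the absence of a row in Table 6.1 is inferred from the stated set.
- If the evaluable condition removes unassessed patients, SAP 2.0 would count them by reason for exclusion and list them. On that reading they would be described. On the likelier reading they would not.
- Counting them as non-responders departs from the no-imputation rule in 1.5. It may also be wrong for individuals, since treatment goal achieved is a listed reason for stopping. This is a reason to show the conservative rate beside the planned one, not in its place.

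**Conclusion.** The concern holds. The only planned response rate and interval are conditional on having been assessed, the protocol names the wider efficacy set, and 6.1 neither counts nor describes the patients left out. The planned rate is too high if unassessed patients respond less often, correct if they respond equally often, and too low if they respond more often. The documents fix neither direction nor size. With 50–80% response and 5–20% unassessed, the extremes run from 16 points too high to 10 points too low. The effect is zero if every patient is assessed. The change is worth making because it is cheap and makes a reference endpoint readable. It does not affect the safety purpose or the enrolment target.

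**What to change.** In SAP 6.1, for each disease:
1. Add a *not assessed* row to the frequency table, in line with the rule for missing categories in 1.5.
2. Report the response rate with its 95% confidence interval over all treated patients with the target disease in efficacy evaluation, counting the unassessed as non-response. Declare this as an exception to the no-imputation rule, and print the assessed-only rate and interval beside it.
3. State in 1.1.2 and 2.0 that patients without a response assessment remain in the efficacy set.
4. Optionally, describe the unassessed by treatment status: completed 16 cycles, discontinued by recorded reason, or died. Reasons for non-assessment are not listed as collected, so they cannot be used.

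The split by PET assessment can stay on assessed patients.

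Items 1 to 3 cost some SAP wording, one row and one line per disease, and no new data. Item 4 costs a little more: death is not a listed discontinuation reason and must be taken from adverse event outcomes, and a patient can have more than one recorded reason, so categories may overlap. The downside is a lower, conservative rate beside the assessed-only one and a declared exception to 1.5.
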